## ANALYSIS POPULATIONS

This study will enroll approximately 300 MF-CTCL patients who are being treated (newly initiated or continuing treatment) with Valchlor from up to 50 participating university-affiliated hospitals, community hospitals, or community clinics in the United States.

Patients considered 'being treated with Valchlor' are composed of two distinct groups:

- 1) Patients who are newly initiating Valchlor treatment (i.e. patients who have initiated Valchlor within 30 days or fewer prior to enrollment) and,
- 2) Patients who are continuing treatment with Valchlor (i.e. patients who have been on Valchlor for more than 30 days prior to enrollment).

Patients in either group must be treated with Valchlor at enrollment to be eligible for the study.

All consecutive MF-CTCL patients who are receiving Valchlor at participating US centers are eligible for enrollment in the study, regardless of other MF-CTCL therapies received before or at the time of enrollment.

The primary efficacy endpoint will be the proportion of subjects who are responders to treatment at the 12-month timepoint using a  $\geq 50\%$  reduction from baseline in BSA as the definition of a responder in the group of patients who used mechlorethamine plus corticosteroids and possibly another treatment. Since PROVe did not require a specific visit schedule, the primary 12-month analysis will include patients with a post-baseline % BSA score that falls within a window of  $365 \pm 90$  days. Please note that in this observational trial, patients continued on study even if they permanently discontinued mechlorethamine gel for any reason and switched to new therapy. Given this, such patients (15-20%) will be excluded from the analysis at 12 months. A sensitivity analysis will be conducted for the primary analysis using the full dataset. We will compare this to the subset of patients who discontinued mechlorethamine gel (Table 21a).

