The by-time analyses for each visit will provide supportive clinical and statistical mechlorethamine response data over the whole treatment period, before and after the 12 month results. Patient visits were variable throughout the study and no defined patient visits were required in PROVe. Given this construct, the By-Visit analyses of % BSA data, Pruritis VAS, Skin-Dex 29, and the MF/SS CTCL QOL instrument will be constructed from the respective change from baseline that occurred closest to each of the following timepoints 1, 3, 6, 9, 12, 15, 18, 21 and 24 months, and will include data that falls within  $\pm 45$  days of each designated timepoint.

Other secondary endpoints include:

- Overall Response Rate 2 (ORR2) Percent of patients with  $\geq 50\%$  reduction from baseline in % Body Surface Area of disease for at least two consecutive visits.
- Overall Response Rate 4 (ORR4) Percent of patients with  $\geq 50\%$  reduction from baseline in % Body Surface Area of disease for at least four consecutive visits.
- Time to Next Treatment (TTNT). TTNT is defined as the median number of days an individual patient stayed on a treatment before starting a new treatment or adding on an additional treatment.
- Rates of on Study Hospitalization
- Pruritis VAS
- SkinDex-29

- MF/SS CTCL – QOL Instrument

For each endpoint, separate analyses will be done for patients contributing data with IA and IB staging, all staged patients, and all patients regardless of staging. As PROVe is an observational study, an Intent-to-Treat (ITT) population analysis is not applicable. There are no cases where an intention to treat was prevented and therefore no potential for a selection bias in the analyses prespecified in this SAP. This results in a total of 51 analysis types as shown in the Figure 1 below.

Figure 1: Analysis Populations for the PROVe Study

	Patients Contributing Data			Totals:
	IA and IB Staging	All Staged	All Patients with and without Staging	
Primary Endpoint	1	1	1	3
9 By-Time Analyses	9	9	9	27
7 Other Secondary Endpoints	7	7	7	21
			Overall Total:	51

These analyses will be applied to following four (4) analysis populations:

1. Valchlor + corticosteroids + possibly another treatment (primary) (V+C+other)
2. Valchlor + phototherapy + possibly another treatment (V+P+other)
3. Valchlor + oral bexarotene + possibly another treatment (V+B+other)
4. Valchlor + any other treatment (V+other)

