A minimum sample size threshold of N=20 subjects will be required to conduct a statistical analysis. This minimum is set to ensure that the effect size measurements for the various endpoints (typically using a within treatment change from baseline approach) are reasonable estimates of the true population values. Prior prospective publications that evaluated mechlorethamine clinical response have had similar sample sizes (Liner K. [Drug Des Devel Ther.](#) 2018 Jan 31;12:241-254). With this analysis filter in place the total number of analyses will be determined after the available sample size for each analysis is established. Summary statistics will be provided for endpoints with sample sizes that range from 10 to 19 patients, and no endpoint values will be provided for endpoints with sample sizes with less than 10 patients with the exception of sub-groups for the by-time analysis.

The primary data set from the pre-analysis sample size assessment was selected as patients who used mechlorethamine plus corticosteroids plus possibly another treatment. For all potential endpoints, there were not adequate numbers of mechlorethamine monotherapy treaters that exceeded the N=20 minimum sample size. The following analysis populations will be applied to the primary and secondary endpoints in the study:

1. Valchlor + corticosteroids + possibly another treatment (primary) (V+C+other)
2. Valchlor + phototherapy + possibly another treatment (V+P+other)
3. Valchlor + oral bexarotene + possibly another treatment (V+B+other)
4. Valchlor + any other treatment (V+other)

These groups were selected prior to conducting any analysis on the basis that there were at least 30 patients who received the concomitant MF-CTCL therapy in combination with Valchlor.

Based on discussions with the principle investigator the section II. and III. analyses will be excluded. The difference between continuing and new mechlorethamine users is on average only 3 months, so the new versus continuing comparisons are not clinically much different.

II. Continuing Mechlorethamine Patients

1. Valchlor + corticosteroids + possibly another treatment (primary)
2. Valchlor + phototherapy + possibly another treatment
3. Valchlor + oral bexarotene + possibly another treatment
4. Valchlor + any other treatment

III. New Mechlorethamine Patients

1. Valchlor + corticosteroids + possibly another treatment (primary)
2. Valchlor + phototherapy + possibly another treatment

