Table 27b. Change from baseline at each timepoint in PRO questionnaires: SkinDex-29

Table 27c. Change from baseline at each timepoint in PRO questionnaires: MF/SS CTCL QOL instrument

Table 28. Other Treatments for MF-CTCL

Therapy	Prior to Mechlorethamine Treatment (N=289) (N/%)	During Mechlorethamine Treatment (N=289) (N/%)	Mean Treatment Duration During PROVe Study
Skin-directed therapy, n (%)	226 (78)	125 (43)	
Phototherapy	143 (49.5)	33 (11)	
UVB/Narrow Band-UVB			
PUVA/UVA-1			
ECP – Therakos (extracorporeal photopheresis)			
Radiation therapy (TSEB)	38 (13)	16 (5.5)	
Chemotherapy (topical) Name the 1 agent	4 (1)	1 (<1)	
Corticosteroids (topical)	165 (57)	88 (30)	
See full list below for reference only			
Retinoid (topical)	39 (13.5)	9 (3)	
Bexarotene			
tazarotene			
adapalene			
Imiquimod (topical)	18 (6)	7 (2)	
Systemic therapy, n (%)	83 (29)	47 (16)	
Chemotherapy (systemic)	18 (6)	11 (4)	
methotrexate			
CHOP (cyclophosphamide + vincristine + Adriamycin + prednisone)			
Liposomal doxorubicin			
gemcitabine			
pentostatin			
Monoclonal Antibodies			
Brentuximab			
Alemtuzamab			
Mogamulizumab			

Interferon			
Retinoids (systemic)	59 (20)	36 (12.5)	
Bexarotene			
HDAC Inhibitors	20 (7)	6 (2)	
Vorinostat			
Remetinostat			
Romidepsin			
Panobinostat			

Listing 1: Serious Adverse Events

Patient ID, AE Date, System Organ Class, Preferred Term, Verbatim Term, Completed/Discontinued, Reason for Discontinuation

Listing 2: Serious Adverse Events Resulting in Death

Patient ID, AE Date, System Organ Class, Preferred Term, Verbatim Term

Listing 3: Adverse Events

Patient ID, AE Date, System Organ Class, Preferred Term, Verbatim Term

Listing 4: Pregnancy

Patient ID, Age, Sex/Gender, Positive Pregnancy Confirmation

Listing 5: Secondary Exposures

Patient ID, Age, Sex/Gender, Positive Secondary Exposure

Listing 6: Patient Disposition

Patient ID, D/C Date, Reason for D/C

Listing 7: Demographic and Baseline Characteristics by Subject and Treatment Group

Patient ID, Age, Gender, Race, MF Stage, Date of First Diag, CAILS, SWAT, %BSA

Listing 8: Efficacy Data (CAILS, SWAT Scores and % Body Surface Area with Response Assessment) by Subject and Treatment Group

Patient ID, Age/Gender/Race MF Stage, Visit Dt, CAILS, CAILS Change, CAILS Response, SWAT, SWAT Change, SWAT Response, %BSA, %BSA Change, %BSA Response

Listing 9: Subjects Who Reported Adverse Events

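### The SAP sets no start date for the co-therapy that defines its analysis groups, so treatment added after baseline can decide who is in the primary analysis; TTNT also lacks a time origin

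*SAP*

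**What the plan says.** The SAP, under ANALYSIS POPULATIONS, sets the primary endpoint as 12-month BSA response "in the group of patients who used mechlorethamine plus corticosteroids and possibly another treatment". Three further groups follow the same pattern, with phototherapy, oral bexarotene, or any other treatment in place of corticosteroids. All four are applied to the primary and every secondary endpoint. The Summary of Primary and Secondary Analyses repeats the primary group and adds no timing.

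- **Selection of the groups.** They were chosen before analysis because "there were at least 30 patients who received the concomitant MF-CTCL therapy in combination with Valchlor".
- **Window.** For BSA, "the primary 12-month analysis will include patients with a post-baseline % BSA score that falls within a window of" 365 ± 90 days.
- **Exclusion at 12 months.** It covers patients who "permanently discontinued mechlorethamine gel for any reason and switched to new therapy". A patient who stays on Valchlor and adds something is not excluded.
- **TTNT.** It is the time a patient "stayed on a treatment before starting a new treatment or adding on an additional treatment". No date is given from which time runs.
- **Dated rule elsewhere.** The section Other MF-CTCL Treatments defines being on a therapy at enrollment from start and stop dates. It does not mention the analysis populations.
- **Bias.** ANALYSIS POPULATIONS also states that the prespecified analyses carry no potential for selection bias.

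**The concern.** Treatment is at the physician's discretion, so co-therapies can be added at any point in follow-up. If a later addition can place a patient in a group, the group is formed partly by what happened after baseline. A patient who did well on Valchlor alone never enters V+C. A patient who needed a steroid later does enter, and brings a BSA result obtained without it. The primary response rate would then be credited to a combination that some patients had not begun at the assessment.

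For TTNT, the addition that makes a patient a member may also be the event that ends the patient's time. Two programmers following the SAP could build different primary populations and different TTNT curves.

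**Working it through.** **1. Which counts meet the 30-patient criterion?** SAP Table 28 already carries counts out of N = 289.

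- During mechlorethamine: corticosteroids 88 (88/289 = 30.4%), systemic retinoids 36 (12.5%), phototherapy 33 (11.4%). The next largest are radiation 16 and systemic chemotherapy 11. Exactly three classes reach 30, and they correspond to the three named groups.
- Prior to mechlorethamine: corticosteroids 165, phototherapy 143, systemic retinoids 59, topical retinoids 39, radiation 38. Five classes reach 30, which does not match.

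The criterion is thus reproduced from the during-treatment column only. The oral bexarotene row is blank, so 36 is an upper limit for V+B.

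**2. Can a late addition count in the primary analysis?** The window is 365 − 90 = day 275 to 365 + 90 = day 455. Take a patient on Valchlor alone at a BSA reading on day 365 who adds a steroid at month 18 and stays on Valchlor. The patient used both treatments, has BSA in the window, and did not stop Valchlor and switch. Nothing in the wording keeps this patient out of V+C.

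**3. Group sizes if membership is fixed at baseline.** Let f be the share of a group that started the co-therapy after baseline. The documents do not give f, so a range is assumed. Size = count × (1 − f); 95% half-width for a proportion = 1.96 × √(0.25/n).

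| f (assumed) | V+C (88) | V+C half-width, points | V+P (33) | Systemic retinoids (36) |
|---|---|---|---|---|
| 0% | 88 | 10.4 | 33 | 36 |
| 10% | 79 | 11.0 | 30 | 32 |
| 25% | 66 | 12.1 | 25 | 27 |
| 50% | 44 | 14.8 | 16 | 18 |
| 75% | 22 | 20.9 | 8 | 9 |

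These are upper limits, before restriction to stage IA/IB and to BSA in the window.

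**4. TTNT if time runs from Valchlor start or enrollment.** Here f is the share that adds the co-therapy after that origin and within follow-up. Each such patient has an event no later than the addition, so the share of patients with no event by the end of follow-up is at most 1 − f.

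To illustrate, assume a hazard of 0.02 per month for any other new therapy, late additions following an exponential with the same hazard truncated at 24 months, and full follow-up.

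- Event share by 24 months = f + (1 − f)(1 − e^(−0.48)) = f + 0.381(1 − f).
- Free at 12 months: e^(−0.24) = 0.787 for those on the co-therapy at time zero. For late adders it is 0.787 × (e^(−0.24) − e^(−0.48))/(1 − e^(−0.48)) = 0.787 × 0.440 = 0.346. The two are weighted by 1 − f and f.

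| f (assumed) | Ceiling 1 − f | Event by 24 months | Free at 12 months | Median, months |
|---|---|---|---|---|
| 0% | 100% | 38% | 79% | not reached |
| 10% | 90% | 44% | 74% | not reached |
| 25% | 75% | 54% | 68% | 21.6 |
| 50% | 50% | 69% | 57% | 14.6 |
| 75% | 25% | 85% | 46% | 10.7 |

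The rate of other new therapy is the same in every row; only the grouping rule moves the results. If time runs from the start of the combination, the addition starts the clock and no event is forced.

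**The case against.** The strongest reply is that the SAP nowhere says that any use during Valchlor qualifies. The sentence on 30 patients explains why groups were selected, not who belongs to them. Table 28 is a descriptive shell that nothing links to the populations. It also sits badly with another SAP statement: 125 patients had skin-directed and 47 systemic therapy during mechlorethamine, so at least 289 − 125 − 47 = 117 had neither, yet the SAP says monotherapy patients were too few against the minimum of 20 for all potential endpoints. The at-enrollment rule may have been intended. All of this stands: the rule is undefined, and a reader who takes any-time use as settled goes beyond the documents. It does not supply the missing date.

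A reader might also infer that TTNT is circular for whole groups and cannot be interpreted. The documents do not support that. Patients on the co-therapy at time zero are unaffected, and staying on a treatment can be read as staying on the combination.

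Nor can one estimate how many additions fall after month 12 by spreading them evenly over 24 months. Patients who had completed one year under the original protocol were not re-consented (Protocol 5.9), and the BSA window runs to day 455. Both lower such a share.

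Finally, p-values are descriptive, and Protocol 5.7.4 says the response summary does not estimate efficacy. That limits the claims to be made. However, the SAP names a primary efficacy endpoint, and a descriptive rate still needs a defined denominator.

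**Conclusion.** The point holds in this form: the SAP does not say when the co-therapy must have started, and its wording allows treatment begun after baseline, or even after the 12-month BSA, to place a patient in the primary group. The at-enrollment rule and the 12-month exclusion do not close the gap, and the SAP's statement that there is no potential for selection bias does not hold for groups formed this way. That any use during Valchlor qualifies is a reasonable inference from the wording and from the match with 88, 33 and 36, not a stated rule.

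For TTNT the problem is conditional. It needs a time origin before the addition, and it touches only patients who add the co-therapy after that origin.

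The size cannot be stated, because the late-adder share is not in the documents. The tables above show what assumed shares would imply; they are not estimates.

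**What to change.** Use the start and stop dates already collected on the treatment logs.

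- **BSA, ORR2/ORR4 and PRO analyses.** Define V+C, V+P and V+B by co-therapy that overlaps Valchlor and is ongoing at one fixed date, the verified baseline. Say how co-therapy begun on the same day as Valchlor is treated.
- **Sensitivity analysis.** Also admit co-therapy started after baseline but before the 12-month BSA. This should not be the main rule: a steroid begun the day before the reading would still qualify, and the rule has no clear meaning for ORR2 and ORR4, which span several visits.
- **TTNT.** State time zero, fix the group by co-therapy ongoing at time zero, and count later additions only as events.
- **Partial dates.** METHODS FOR HANDLING MISSING DATA moves a medication date imputed before Valchlor start to the day after Valchlor start. Check that this does not turn an existing co-therapy into a late addition.
- **Reporting.** Show how many patients leave each group, and withdraw the statement on selection bias.

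The cost is SAP wording, a date filter, and smaller groups. With an assumed half of members starting late, phototherapy would be 16 and systemic retinoids 18. Both are below the minimum of 20, so the SAP would allow summary statistics only. At three quarters they would be 8 and 9, below the SAP's limit of 10 for giving endpoint values (by-time subgroups excepted).

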5.2 Population (setting and study population)

This study will enroll approximately 300 MF-CTCL patients being treated (newly initiated or continuing treatment) with Valchlor [see Section 5.2.1 for details] from up to 50 participating centers/clinics in university-affiliated or community hospitals.

Patients considered ‘being treated with Valchlor’ is comprised of two distinct groups: 1) Patients newly initiating Valchlor. These are patients who are enrolled at their first office visit after having initiated Valchlor; 2) Patients continuing treatment with Valchlor. Patients must be actively taking Valchlor on the day of enrollment.

All consecutive MF-CTCL patients being treated with Valchlor [see Section 5.2.1 for details] seen at the participating centers are eligible for enrollment in the study, regardless of other MF-CTCL therapies received before or at the time of enrollment.

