5.4 Data sources

Data elements to be collected include the following: patient demographics, personal and family medical history, including MF-CTCL diagnosis date and etiology, current and historical MF-CTCL treatments, clinical status (as assessed by the physician), and which assessments were used to define response, MF-CTCL-related healthcare utilization (as assessed by the physician), AEs and SAEs whether or not related to Valchlor, deaths, patient-completed symptoms and QOL questionnaires. [Table 1](#) provides an overview of the variables collected at enrollment and during the observation period [see [Section 5.3.2](#) for definition]. For patients who do not have any visits, an affirmative response that the patient is still under care by the site will be requested quarterly, so that the absence of reported assessments can be interpreted the same as the absence of actual assessments.

Since this is a real-world, observational study, there are a number of sources of bias that could potentially affect any conclusions that may be drawn. The methods used to minimize these sources of bias in this study are detailed below [see [Section 5.9](#)].

Therapies specific to MF-CTCL during the course of this study are under the direction of the participating physician and not the study protocol. As this study collects data on both incident patients and prevalent patients, it is necessary to include the date of diagnosis in the data collection forms, in order to minimize potential survivor bias effect.

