5.5 Study size

This study will have an approximate enrollment of 300 patients diagnosed with MF-CTCL who are being treated with Valchlor (newly initiated or continuing treatment).

A sample size of 270 evaluable patients is needed to estimate the percentage of patients with clinical status and the percentage of patients with hospitalizations, both with a margin of error of 6 percentage points. Assuming that up to 10% of patients may be non-evaluable due to incomplete follow-up, the sample size target for enrollment should be 300.

It is projected that approximately 200 evaluable patients will be re-consented under Amendment 1. The margin of error for 200 evaluable patients will be 7%.

Additionally, it is important to be able to estimate these same percentages with a margin of error of 10 percentage points or less for key subgroups representing a third or more of the patient population (e.g., patients newly initiating Valchlor). A total of 100 patients are required to achieve a margin of error of 10 percentage points per subgroup, so that a total enrollment of 300 patients is needed.

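### An average three-month gap does not justify pooling new and continuing Valchlor users, and the SAP also drops the protocol's new-user discontinuation analysis

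*SAP*

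**What the plan says.** The protocol treats new and continuing users as distinct groups. Section 5.5 sets a target half-width of at most 10 points "for key subgroups representing a third or more of the patient population (e.g., patients newly initiating Valchlor"). Sections 5.7.1 to 5.7.3 split demographics, clinical characteristics, prior treatments, past assessment methods and treatment patterns by the two groups. Section 5.7.3 also plans Kaplan-Meier estimates of freedom from Valchlor discontinuation, in newly initiated patients only.

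The SAP (Analysis Populations) lists the same four combination-therapy populations for continuing and for new users, then excludes both sets after discussion with the investigator because "The difference between continuing and new mechlorethamine users is on average only 3 months". It gives no standard deviation, range or group sizes. Its Summary of Primary and Secondary Analyses combines continuing and new users in the primary endpoint. Statistical Methods reports demographics and clinical characteristics overall. No Kaplan-Meier analysis of Valchlor discontinuation appears in the SAP.

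The split is not gone everywhere. The SAP text keeps it for hospitalization and emergency room rates (Healthcare Resource Utilization) and for the pruritus VAS and Skindex-29 (Statistical Methods).

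The definitions differ. In protocol section 5.2, on new initiators: "These are patients who are enrolled at their first office visit after having initiated Valchlor". In the SAP, new users are "patients who have initiated Valchlor within 30 days or fewer prior to enrollment".

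**The concern.** The reason given for pooling concerns average time on drug. The difficulty with prevalent users is who is left to enrol. The SAP requires every patient to be on Valchlor at enrollment and defines continuing users as more than 30 days past initiation. A starter who stopped in that period, for intolerance or lack of benefit, can never be counted as continuing. A mean difference of three months, or any other length, says nothing about how many were lost that way.

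The distinction also bears on the primary endpoint. The SAP's Assessment Schedule warns that an enrollment BSA may not be a true baseline for someone already using mechlorethamine, which is the situation of continuing users. Elsewhere the SAP states that its prespecified analyses carry no potential for selection bias.

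Both documents give tolerability and discontinuation as part of the study's rationale. Without a new-user analysis the report cannot show how starters fare in the first months.

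**Working it through.** **1. The protocol's precision figures.** Inputs from section 5.5: 270 evaluable patients for clinical status and hospitalization, "both with a margin of error of 6 percentage points"; 200 for 7 points; 100 per subgroup for 10 points; and "Assuming that up to 10% of patients may be non-evaluable due to incomplete follow-up". The confidence level and proportion are not stated; two-sided 95% and p = 0.5 are assumed.

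n = 1.96² × 0.25 / m² = 0.9604 / m²

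- m = 0.06: 266.8, so 267 (stated 270)
- m = 0.07: 196.0, so 196 (stated 200)
- m = 0.10: 96.04, so 97 (stated 100)
- 270 / 0.9 = 300 enrolled, and 300 / 3 = 100 in a one-third subgroup

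The figures reproduce. One third of 300 less 10% leaves 90 evaluable, which gives 0.98 / √90 = ±10.3 points, just over the target.

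**2. The two documents side by side.**

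| Item | Protocol | SAP |
|---|---|---|
| New user | First office visit after initiation | 30 days or fewer since initiation |
| Demographics, clinical characteristics | Overall and by new/continuing | Overall; shells by combination therapy |
| Time to Valchlor discontinuation | Kaplan-Meier, new users only | Absent |
| Primary BSA response | Not a protocol endpoint | New and continuing pooled |
| Hospitalization and ER rates | No split in 5.7.4 | Split in text; Table 16 shell has combination-therapy columns only |
| VAS, Skindex-29 | By responder status | Split in text and in the Table 17aa/17ab titles; shells have no such columns |
| Adverse events | No split | No split |

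A patient first seen six weeks after starting Valchlor is new under the protocol and continuing under the SAP.

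**3. Whether a three-month gap is harmless.** This is an illustration only. Suppose a fraction D of starters stops by month 12, with Weibull cumulative hazard H(t) = −ln(1 − D) × (t/12)^k. Let continuing users enter at month 3 and be followed for 12 months. Their on-study discontinuation is 1 − exp{−[H(15) − H(3)]}. D = 15-20% is borrowed from the SAP as an anchor, and one third new users is assumed.

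| Quantity | Constant hazard (k = 1) | Front-loaded (k = 0.5) |
|---|---|---|
| Starters stopping by month 3 | 4.0-5.4% | 7.8-10.6% |
| Continuing users, 12 on-study months | 15-20% | 9.6-12.9% |
| Pool, one third new | 15-20% | 11.4-15.3% |

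For example, with D = 0.15 and k = 0.5: H(12) = 0.1625, H(3) = 0.0813 and H(15) = 0.1817. Continuing users show 1 − exp(−0.1004) = 9.6%, and the pool is 15/3 + 9.6 × 2/3 = 11.4%.

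The same three-month gap is harmless under one hazard and material under the other. The mean gap alone cannot distinguish them.

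**4. Precision of restored new-user results.** Half-width = 0.98 / √n. The share of new users is not stated; one third to one half is assumed.

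- Whole cohort, 200 evaluable: 67 to 100 new users, ±12.0 to ±9.8 points.
- Topical corticosteroid users during Valchlor: 88 of 289 (SAP Table 28). Removing the 15-20% who discontinued and switched leaves 70.4 to 74.8. One third of 70.4 is 23.5 (±20.2 points); one half of 74.8 is 37.4 (±16.0 points). Restriction to stage IA/IB and to patients with BSA in the 12-month window would reduce these further.

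**The case against.** The strongest reply is that the protocol promised less than it may seem to. New initiators are only an example of a key subgroup. Section 5.7.5 never stratified adverse events, and section 5.7.4 does not stratify response and disclaims any estimate of efficacy. BSA response by combination therapy was introduced by the SAP. The objectives concern patients treated with Valchlor, not starters alone. New-user rows in the corticosteroid group would be imprecise, and pooled exposure and discontinuation data remain in Tables 1C, 17b and 20. All of this stands. It limits the departure from the protocol to the missing Kaplan-Meier analysis, the lost split in demographics and clinical characteristics, and the new-initiator subgroup precision. It does not make the three-month argument valid.

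Four stronger readings are tempting and are not supported:

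- *Pooling inflates response.* The direction depends on baseline handling. If an already improved enrollment BSA served as baseline, response in continuing users could be understated.
- *Pooling lowers dermatitis incidence.* This is plausible but not shown. Table 18 counts events ongoing at enrollment, so unresolved early reactions in continuing users are included. The lack of a split comes from both documents.
- *15-20% of starters stop by 12 months.* The SAP figure describes patients who permanently discontinued and switched therapy. It is not a cumulative stopping rate from initiation.
- *The protocol recognised selection on tolerating Valchlor.* Section 5.4 collects the date of diagnosis "in order to minimize potential survivor bias effect"; it does not address time since Valchlor start.

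**Conclusion.** The point holds as a defect of justification and of consistency. The stated reason does not support pooling, the protocol's new-user discontinuation analysis has been lost, the two definitions of a new user conflict, and the SAP text and shells disagree on where the split applies. It should be corrected.

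The size of any bias is unknown. The illustration runs from no effect under a constant hazard to a pooled 11.4-15.3% in place of 15-20% under a front-loaded one. It rests on an assumed hazard shape, entry at month 3, one third new users and a borrowed anchor. It shows that the answer depends on data the SAP does not plan to display; it is not an estimate for this study. To say that early discontinuation or early reactions are hidden would go too far, because the pooled tables remain.

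**What to change.** 1. Use one definition of newly initiating in both documents, computed from the recorded Valchlor start date.
2. Restore the Kaplan-Meier analysis of Valchlor discontinuation in new users, whole cohort, and state its time origin. If time runs from the Valchlor start date, treat enrollment as delayed entry, since new users must also be on drug when enrolled.
3. Add new and continuing rows to Table 21, Table 21a and the ORR tables (23 and 24), whole cohort first and then V+C+Other, under the SAP's existing rules (analysis at 20 or more patients, summary statistics only at 10 to 19). Table 21a matters because the main 12-month analysis excludes patients who discontinued and switched, so a new-user row in Table 21 alone would omit those who stopped early and switched.
4. Restore the split for demographics and clinical characteristics. Add it to the adverse event and dermatitis summaries as an improvement on both documents.
5. Give the Table 16 and 17aa/17ab shells the columns that the SAP text promises.
6. Replace the three-month sentence with the distribution of time on Valchlor at enrollment and the two group sizes.

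The cost is programming and additional table rows from data already collected. New-user estimates will be imprecise, as shown in the working, and some rows will fall below 20 patients. The restored analyses should be presented as descriptive.
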